10.1.1.2. General Statistical Procedures

The statistical analyses will be divided into four main parts (P1 to P4): descriptive, univariate, multivariate and exploratory. The descriptive part intends to describe the data by generating a set of statistical summaries of each patient-vector entry. The univariate analysis will investigate the link between each patient-vector entry and the treatment response (as described by the pain evolution). All the statistical procedures will further be described in a dedicated SAP.

P1 - Data Description

P11: Data pre-processing and summary.

Classical statistical information will be computed for each input feature (mean, median, standard deviation). A log-transform will be applied to some features, when appropriate.

P12: Missing values management.

The number of missing values will be reported for each feature. In subsequent analyses, value imputation might be performed if needed. Such cases will be documented.

P13: Outlier detection.

Population outliers will be detected through a Principal Component Analysis (PCA) visualization. Outliers might be removed for at least parts of the further analyses. Such cases will be documented.

P2 - Univariate Analysis

P21: Features Impact Assessment.

The correlation between each feature and the treatment response in terms of target feature will be assessed.

For each test performed in P2, if a non-conclusive p-value is obtained and when possible, an estimation of the required sample size will be performed based on the study data.

P3 - Multivariate Analysis

The aims of the multivariate analysis are i) to explore links between features (including all input and target features), ii) to predict target features based on input features, iii) to identify most important input features for this predictive task.

P4 - Exploratory Analysis

P41 - New populations identification.

We identify subgroups of patients with intra-group similar pain evolution curves, and inter-group different pain evolution curves. We define new “class labels” accordingly. If coherent profiles are found, we might consider applying a modeling procedure similar to P3.

P42 – Genetic data exploitation.

In case the genetic material from patients is used, similar experiments as those described above might be performed to discover links between genetic traits (snips for example) and pain evolution or pain treatments efficacy.

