2.2 Secondary Objectives

- 1. To identify groups of patients showing similar profile at baseline, in terms of personality traits and disease history
- 2. To measure the concordance between questionnaire-based and clinical pain assessment
- 3. To identify typical evolution of pain level among cancer patients with bone metastases

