4.2 Study Participant Characteristics

The following variables will be recorded and may be used as quantitative or classification variables:

- Patient characteristics, measured at V1:
 - Study center
 - Patient's sociodemographic characteristics: age, sex and other demographic characteristics
 - Recent analgesic treatment history
 - Personality questionnaires, at facet- and domain-level: Multidimensional Health Locus of Control Scale (MHLCS, with domains I, C and P), Hospital Anxiety and Depression Scale (HADS), Revised Life Orientation Test (LOT-R) and Expectation.
 - Pain evaluation questionnaires: Douleur Neuropathique en 4 questions (DN4), Neuropathic Pain Symptom Inventory (NPSI), and Pain Catastrophizing Scale (PCS)
- Pain and quality of life assessment, measured at V1 and V2:
 - Brief Pain Inventory (BPI)
 - Quality of Life questionnaire in 30 questions (QLQ-C30), IGAC, PGAC
 - Clinical Pain Assessment (CPA): Static Allodynia (SA), Dynamic Mechanical Allodynia (DMA), Mechanical Pain Threshold (MPT), Thermal Pain Sensitivity (TPS)
- Follow-up from the daily diary and intermediate visit:
 - Daily Average and Worst Pain Score (APS and WPS),
 - Daily analgesic therapy (including rescue medication): number of distinct drugs intaken, number of distinct drug categories intaken
 - Intake of rescue analgesic treatment if any,

Note that the description of analgesic therapy hereabove requires the grouping of drugs into a small number of classes which will be described in the Statistical Analysis Report.

The collection of the values of all these variables and variables derived from them for a single patient is referred to as *the patient-vector* below in the text.

5 Description of the Analyses

The final statistical analysis covers four aspects (Ax) detailed in the following sections:

- A1: Descriptive statistics at baseline, covering secondary objectives number 1 and 2.
- A2: Evolution of daily pain and treatments, covering secondary objective number 3.
- A3: Prediction of treatment efficacy, covering the primary objective

In addition, the interim statistical analysis will cover the following two aspects, corresponding to the interim objectives:

- I1: Sample size computation for the prediction of treatment efficacy.
- I2: Relation between psychological traits and pain evolution

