5.1 A1: Descriptive statistics at baseline

This section provides general information useful before starting any data analysis. Only variables at baseline are analysed at this point, so that any decisions taken are not influenced by the observed response to treatment. The variables covered are: sociodemographic characteristics, recent analgesic treatment history, personality questionnaires, pain (including CPA) and quality of life at visit 1.

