5.1.3 A1.3: Outlier detection and clustering

Population outliers will be detected through a principal component analysis (PCA) visualization, reported in Figure (1). The percentage of variance captured will be documented. The patients will be colored by their study center in order to detect possible differences among the centers.

Outliers might be removed for at least parts of the further analyses. Such cases will be documented.

A clustering procedure, namely an ensemble k-Means, will be applied in order to identify subgroups of patients with intra-group similar variables at baseline, and inter-group different variables at baseline. Table (tab-v1-clustering-desc) will report per-cluster univariate statistics (median, first and third quartiles) for all variables used in the clustering procedure.

A1.4: Correlation analysis 5.1.4

The correlation between each variable (personality traits and sociodemographic variables) and the pain at baseline (APS, WPS, BPI severity, interference and QLQ-C30) will be assessed. Statistical tests for non-zero Spearman's correlation will be used. For categorial variables, exact Fisher tests will be used. Correction for multiple testing will be applied. Results will be reported in Table (tab-v1-correlations) and Figure (2). Scatterplots of the significant correlations will be produced. Figure (3) will detail the correlations within pain assessment variables and Figure (4) the correlations between personality traits and pain assessment.

5.2A2: Evolution of daily pain and treatments

Pain evolution will first be analysed on its own (secondary objective 3, i.e. without linking it to the evolution of treatments). Then, the evolution of analgesic therapies are studied, as well as their correlation with pain evolution. Due to the complexity of treatments combinations for each patient and their frequent adaptation during the follow-up period, this analysis will be made on a simple summary of the therapy evolution. Finally, the interest of each variable characterizing the patient at baseline is evaluated for its relation with the pain evolution profile.

A2.1: Summary of individual pain evolution 5.2.1

Feature extraction will be performed in order to summarize each per-patient APS evolution curve into 3 meaningful variables:

- mean APS value
- linear trend of APS
- variability of APS around trend

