6.2 Figures

Figure 1: Outlier detection by Principal Component Analysis based on data at baseline. The two first components are represented (Variance captured: %). Colors indicate the grouping of points into clusters.

Figure 2: Matrix of correlations between all pairs of variables at baseline (personality traits and sociodemographic variables)

Figure 3: Scatterplots of the significant correlations between the different pain measures at baseline

Figure 4: Scatterplots of the significant correlations between a personality trait and a pain measure at baseline

Figure 5: Summary visualization of the evolution of pain during follow-up period. Each point represents a patient, with average APS as abscissa and linear trend as ordinate

Figure 6: Summary visualization of the evolution of analgesic treatments during follow-up period. Each point represents a patient, with the number of different analgesic drugs (for the graph on the left) or the number of different analgesic drug classes (on the right) as abscissa, and their linear trend as ordinate

Figure 7: Learning curve for the prediction of analgesic treatment efficacy. The average performance evaluated by cross-validation on random subsets of the data is shown in ordinate, with the size of the training set as abscissa. An extrapolation curve (LOWESS) is also shown for sample sizes up to N=200.

7 Data Transfer and Unblinding Plan

The study data is collected and managed by Aepodia SA. Several information transfers will occur between Aepodia and DNAlytics, under the supervision of Tools4Patient:

Jun. 2015 **Database table structure transfer** – The objective of this transfer is to allow DNAlytics to prepare the analysis scripts and finalize the SAP. The data concerning a few included patients will be transfered in order to make the scripts creation possible. Those patients data are anonymized by Aepodia prior to the transfer to DNAlytics. Those patients will however be identified by their inclusion number.

	T2001-01 – Statistical Analysis Plan	
DNAIUtics Deterdriven personalized medicine from R&D to market access		To : T4P Auth. : [name] V1.3 - 2017-04-10

May 2017 (Est.) Interim database transfer – The objective of this transfer from Aepodia to DNAlytics is to apply the interim analysis plan described in this document. Those patients data are anonymized by Aepodia prior to the transfer to DNAlytics. Those patients will however be identified by their inclusion number.

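### The clustering step that answers secondary objective 1 has no way to report that no distinct patient groups were found

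*SAP*

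**What the plan says.** SAP 2.2 states secondary objective 1: "To identify groups of patients showing similar profile at baseline, in terms of personality traits and disease history". The list that opens SAP section 5 assigns it to an analysis: "A1: Descriptive statistics at baseline, covering secondary objectives number 1 and 2". Within A1, only section 5.1.3 forms groups: "A clustering procedure, namely an ensemble k-Means, will be applied in order to identify subgroups of patients with intra-group similar variables at baseline".

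Two outputs are planned. One is a table: "Table (tab-v1-clustering-desc) will report per-cluster univariate statistics (median, first and third quartiles) for all variables used in the clustering procedure". The other is the principal component plot, whose legend in SAP 6.2 reads: "The two first components are represented (Variance captured: %). Colors indicate the grouping of points into clusters". The text of 5.1.3 colours that same plot by study centre, so the two places need to be reconciled.

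The candidate inputs are in SAP 5.1: "The variables covered are: sociodemographic characteristics, recent analgesic treatment history, personality questionnaires, pain (including CPA) and quality of life at visit 1". Which of these enter the clustering is not said.

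The SAP does not give k, a rule for choosing k, the recipe for combining the ensemble runs, a one-group outcome, a measure of separation or stability, or a comparison with data that contain no groups. The table template file named in SAP 6.1 was not available for this review.

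**The concern.** For a given k of 2 or more, k-means looks for the split with the smallest within-cluster sum of squares. Such a split exists for any sample, including one drawn from a single homogeneous population. The planned table then compares the clusters on the same variables that were used to form them, so differing medians are built in.

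Other steps in A1 and A2 that look for structure can come out negative. The correlations in SAP 5.1.4 are tested with a multiplicity correction, and the overall pain trend in SAP 5.2.1 has a signed rank test. Objective 1 has no counterpart. If traits such as anxiety, optimism or catastrophizing vary smoothly from patient to patient, the report will still show two or more types with visibly different profiles, and objective 1 will read as achieved. Nothing in the plan leads to the opposite sentence.

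**Working it through.** The documents state no figure for the clustering, and protocol 4.2.1 bases the sample size on no formula, so there is nothing to reproduce. The check is a simulation.

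**Inputs from the documents:** about 140 completers (protocol 4.2.1), the population on which the SAP bases its analyses (SAP 4).

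**Assumptions:** 20 standardised variables; pairwise correlation r of 0 or 0.3; k = 2, 3 or 4; 20 datasets per setting. The ensemble is 40 k-means runs on 80% subsamples, combined through the proportion of runs in which two patients fall together, with average linkage cut at k. No-group data come from one multivariate normal population. The contrast case has three true groups, each shifted by 2.5 SD on its own third of the variables, with r = 0 within groups.

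**Step 1: can the step return no groups?** Let W(k) be the within-cluster sum of squares and T = W(1) the total. For k of 2 or more, W(k) < T for any sample with enough distinct points, so a split is always available. Exactly k groups came back in every run.

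**Step 2: does the planned table separate the two cases?** For each dataset, take the range of cluster medians for each variable and keep the largest; then average over datasets. A patient pair is ambiguous if it falls together in more than 10% and less than 90% of the runs that contain both.

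| Data | k | Largest median gap (SD) | Mean silhouette | Ambiguous pairs |
|---|---|---|---|---|
| No groups, r = 0 | 2 | 1.01 | 0.052 | 91% |
| No groups, r = 0 | 3 | 1.32 | 0.041 | 88% |
| No groups, r = 0 | 4 | 1.62 | 0.039 | 77% |
| No groups, r = 0.3 | 2 | 1.23 | 0.174 | 13% |
| No groups, r = 0.3 | 3 | 1.82 | 0.107 | 29% |
| No groups, r = 0.3 | 4 | 2.10 | 0.070 | 44% |
| Three true groups, r = 0 | 3 | 1.91 | 0.365 | 0% |

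The third column is the kind of evidence the SAP plans to show. Its value with three true groups (1.91) lies inside the range for no groups (1.01 to 2.10). The silhouette, which the SAP does not plan, differs clearly. The ensemble alone is no safeguard: with correlated ungrouped data and k = 2, only 13% of pairs were ambiguous, so the split looks stable. Results with 40 variables were similar.

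**Step 3: is a negative answer attainable?** Two rules were tried at n = 140 with 20 variables.

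- *Gap statistic.* Gap(k) = mean of log W(k) in reference data minus log W(k) observed. Take the smallest k with Gap(k) at least Gap(k+1) minus its simulation error, for k = 1 to 4. It chose one group in 20/20 no-group datasets at r = 0 and 20/20 at r = 0.3, and k = 3 in 20/20 with three true groups. It was not tried on true groups with correlated variables.
- *Cluster index against a single population.* Compare W(k)/T with its distribution in data simulated from one multivariate normal with the observed covariance. It declared groups falsely in 0/20 at r = 0 and 0/20 at r = 0.3. With 0/20, the one-sided 95% upper limit is 1 − 0.05^(1/20) = 13.9%, so this supports control of false claims without proving 5%.

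**Step 4: what does the second rule miss?** At r = 0.3 it detected two real groups in 0/20 (1.5 SD apart on 10 of the 20 variables), 0/20 (2 SD on 5) and 1/20 (2 SD on 10). A separate run of the first setting gave 0/40. Together that is 0/60, with upper limit 1 − 0.05^(1/60) = 4.9%. The likely reason is that the reference covariance is estimated from the same data and already contains the spread caused by the groups.

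**Step 5: when does it claim too much?** On no-group data, with each k from 2 to 4 judged separately, groups were declared for at least one k in 62.5% of datasets (unscaled, one dominant skewed variable), 37.5% (unscaled 0–100 four-level items) and 20% to 60% (standardised, strong floor effects, correlation 0.5 to 0.6). With standardised variables and correlation up to 0.3, the rate stayed at or below 5%.

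**The case against.** The strongest reply is that A1 is descriptive. SAP 1.3 treats the secondary objectives as intermediate milestones, and a partition with its medians does tell a reader how the sample can be divided. That stands for the table as description. It does not stand for the objective, which is to identify groups: describing a forced split does not show that there was anything to split.

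The plot is a fair second point. Well-separated clusters may be visible on two components, so the table is not the only evidence. But the SAP gives no criterion for reading the plot, and the two descriptions of its colouring differ.

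Third, the ensemble recipe is open. Some variants can return a single group, and the missing template might fix k. The SAP names no such variant, however, and a fixed k of 2 or more would still leave no negative outcome.

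A reader might also infer that the SAP departs from the protocol, because part P41 says: "If coherent profiles are found, we might consider applying a modeling procedure similar to P3". The documents do not support that. P41 concerns pain-evolution curves, not baseline profiles, and it makes only the later modelling conditional, not the forming of subgroups. Nor does the SAP plan significance tests between clusters, so it cannot be faulted for misleading p-values there.

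**Conclusion.** The concern holds in a limited form. Followed as written with k of 2 or more and a consensus cut at k, SAP 5.1.3 divides ungrouped data and cannot report that no distinct groups were found. In the simulated settings, median gaps of 1.0 to 2.1 SD arise with no groups, against 1.9 SD with three true groups. These sizes rest on the assumed number of variables, correlation, k and ensemble recipe. The absence of a negative outcome rests only on k being at least 2 and the cut being made at k.

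Three stronger readings are tempting and should be resisted.

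- That the result is certain and empty: one-group ensemble variants exist, and the medians still describe the partition. What lacks support is the claim that groups exist.
- That the primary objective or patient stratification is compromised: A2.3 and A3 use baseline characteristics directly, and no section carries the clusters forward.
- That failing a reference check would show patients lie on a continuum: given the detection rates in step 4, it would not.

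The point deserves a SAP change because objective 1 is a named objective and the remedy is cheap. It does not threaten the study's main analysis.

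**What to change.** Add to SAP 5.1.3, in wording such as:

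> The clustering variables are listed, transformed where skewed (see 5.1.1) and standardised. One group (k = 1) is an allowed outcome. For a prespecified range of k, the ratio of within-cluster to total sum of squares is compared with its distribution in at least 500 datasets simulated from a single population with the observed covariance. One overall 5% criterion applies across all k. Distinct groups are claimed for secondary objective 1 only if it is met. Otherwise the report states that no evidence of distinct groups was found, and tab-v1-clustering-desc is labelled a descriptive partition.

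The overall criterion can be built by taking the most extreme standardised index across k and comparing it with the same quantity in each simulated dataset. A gap statistic that includes k = 1 is an acceptable alternative. Its power with correlated variables should be checked before it is chosen.

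The cost is a few SAP sentences and lines of R, with no new data. There are two downsides to state in the SAP. Power is low when variables are correlated, so a negative result is inconclusive and must not be worded as absence of groups. And strong floor effects combined with high correlation can still inflate false claims: a single criterion across k removes the multiplicity part of this, not the part due to distributional shape. Variables with many floor values should therefore be examined before they enter the clustering.

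### The only clustering step for secondary objective 1 does not restrict its inputs to personality and disease history, and the SAP lists no disease-history variables, so the groups may reflect pain severity

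*SAP*

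**What the plan says.** SAP 2.2 states secondary objective 1 as: "To identify groups of patients showing similar profile at baseline, in terms of personality traits and disease history". The list opening SAP section 5 gives that objective to "A1: Descriptive statistics at baseline, covering secondary objectives number 1 and 2".

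SAP 5.1 sets the variables for the whole of A1: "sociodemographic characteristics, recent analgesic treatment history, personality questionnaires, pain (including CPA) and quality of life at visit 1".

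A1.3 (SAP 5.1.3) holds the only clustering step in A1. It applies an ensemble k-means to "identify subgroups of patients with intra-group similar variables at baseline, and inter-group different variables at baseline". It gives no input list, number of clusters, scaling or coding rule. The table tab-v1-clustering-desc then gives medians and quartiles per cluster "for all variables used in the clustering procedure".

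The patient-vector in SAP 4.2 contains centre, sociodemographics, recent analgesic history, personality, pain and quality-of-life measures and diary data. It has no disease-history entry. Protocol 4.1.1 and Attachment 2 (16.2) do collect primary disease and relevant medical history, and primary disease treatment history, at enrolment.

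**The concern.** The objective and the analysis assigned to it name different variables, and the mismatch runs both ways. The A1 scope adds pain, CPA and quality of life, which objective 1 does not ask for. It leaves out disease history, which is half of what objective 1 does ask for.

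The first part matters because k-means weights standardised inputs equally, and a large block of correlated scores can set the main direction of the split. If the pain and quality-of-life scores share a severity component, the reported profiles could be high-pain and low-pain groups, and real personality groups could go unseen. The second part matters because dropping the pain variables would not be enough: the SAP still defines nothing to represent disease history.

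**Working it through.** The documents give no figure for the clustering, and Protocol 4.2.1 says the sample size came from no hypothesis test or precision target. There is nothing to reproduce, so the check is textual plus an illustration.

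**1. Objective against scope**

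| Variable group | Objective 1 (SAP 2.2) | A1 scope (SAP 5.1) | Patient-vector (SAP 4.2) |
|---|---|---|---|
| Personality | yes | yes | yes |
| Disease history | yes | no | no |
| Recent analgesic history | no | yes | yes |
| Sociodemographics | no | yes | yes |
| Pain, CPA, quality of life | no | yes | yes |

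**2. Count of scores, following the SAP 4.2 grouping**

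- Personality: MHLCS 3 + HADS 2 + LOT-R 1 + Expectation 2 = 8.
- Pain and quality of life: DN4 1 + NPSI 5 + PCS 3 + BPI 2 + IGAC/PGAC 2 + APS/WPS 2 + CPA 5 + QLQ-C30 4 (an assumed minimum) = 24.
- Personality share: 8/32 = 25%. If PCS is moved to personality: 11/32 = 34%.

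**3. Why block size matters**

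Two-cluster k-means on standardised data tends to cut along the leading principal component. For p scores with common correlation r, the leading eigenvalue is 1 + (p − 1)r. Two equal groups d SD apart on every score induce r = (d²/4)/(1 + d²/4).

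- Personality, p = 8, d = 1.0: r = 0.25/1.25 = 0.20; eigenvalue 1 + 7 × 0.20 = 2.40.
- Personality, p = 8, d = 1.5: r = 0.5625/1.5625 = 0.36; eigenvalue 1 + 7 × 0.36 = 3.52.
- Pain and quality of life, p = 24: 1 + 23r equals 2.40 at r = 1.40/23 = 0.06, and 3.52 at r = 2.52/23 = 0.11.

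With 24 scores on one factor, a common correlation of roughly 0.06 to 0.11 already matches the personality block. This is a guide, not an exact threshold, because a truly two-group direction gains somewhat more from a split than a bell-shaped one.

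**4. Simulation**

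Assumptions: 140 patients, plain k-means with k = 2, standardised scores, 8 starts, 150 data sets per setting. There are 8 personality scores with two true groups d SD apart, and 8 or 24 pain/quality-of-life scores on one factor with common correlation r. Agreement is the adjusted Rand index (ARI; 0 = chance, 1 = perfect). Ranges span a correlation of 0 to 0.3 between personality group and severity.

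| d | Pain/QoL scores | r | Pain/QoL eigenvalue | ARI, personality groups | ARI, severity median split |
|---|---|---|---|---|---|
| 1.0 | 24 | 0.1 | 3.3 | 0.11–0.28 | 0.29–0.31 |
| 1.0 | 24 | 0.2 | 5.6 | 0.01–0.12 | 0.52–0.53 |
| 1.0 | 24 | 0.5 | 12.5 | 0.00–0.07 | 0.70–0.71 |
| 1.5 | 24 | 0.1 | 3.3 | 0.84–0.90 | 0.01–0.09 |
| 1.5 | 24 | 0.2 | 5.6 | 0.06–0.27 | 0.43–0.50 |
| 1.5 | 24 | 0.5 | 12.5 | 0.01–0.10 | 0.68–0.70 |
| 1.0 | 8 | 0.1 | 1.7 | 0.66–0.67 | 0.00–0.07 |
| 1.0 | 8 | 0.5 | 4.5 | 0.02–0.17 | 0.52–0.56 |
| 1.5 | 8 | 0.1–0.3 | 1.7–3.1 | 0.87–0.93 | 0.00–0.09 |
| 1.5 | 8 | 0.5 | 4.5 | 0.41–0.60 | 0.24–0.30 |

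Clustering the 8 personality scores alone gives ARI of about 0.70 at d = 1.0 and 0.93 at d = 1.5, whatever the pain data look like.

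**5. More than one pain factor** (d = 1.2, loading 0.55)

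- 12 personality and 20 pain scores: ARI with the personality groups is 0.04 with one pain factor and 0.65–0.89 with four.
- 8 personality and 20 pain scores, four factors: 0.69, 0.28 and 0.04 at inter-factor correlations of 0, 0.3 and 0.5.
- 8 personality and 24 pain/quality-of-life scores: 0.83 on personality alone, falling to 0.00–0.07 with one factor, or with four factors correlated 0.3–0.5.

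**The case against.** **The SAP does not say that all baseline variables are clustered.** This is correct, and a reader might wrongly infer that it does. The 5.1 list covers all of A1, which also serves objective 2 (questionnaire against clinical pain assessment), so pain and CPA have to be in it. The caption of Figure 2 also uses the phrase narrowly: "Matrix of correlations between all pairs of variables at baseline (personality traits and sociodemographic variables"). But that narrowing is made by an explicit parenthesis, and A1.4 carries a similar one; A1.3 has none. Even the Figure 2 set would not fit objective 1, because it adds sociodemographics and lacks disease history.

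**Severity groups are not a certain result.** This stands too. The documents give no correlations. Protocol 3.2 describes mixed nociceptive and neuropathic pain, and Protocol 8.2.3.2 gives the NPSI five dimensions, so a single severity factor is only one possibility. With several weakly related factors, or few pain scores, personality groups often survive. The simulation also uses plain k-means with k = 2 rather than the planned ensemble version.

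**The harm is limited.** Largely true. The clustering carries no test and feeds no endpoint. A reader might infer that pain-based clusters would later be used to explain pain. The documents do not support that: A2.3 and A3 use individual baseline characteristics and name no cluster labels. A severity split would also show in tab-v1-clustering-desc. Seeing it there, however, would not supply the groups that objective 1 asks for.

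**Conclusion.** The point holds as a mismatch between an objective and its only analysis, which is more than missing detail. A1.3 leaves its inputs unrestricted under a scope that includes pain, CPA and quality of life, and disease history is in neither SAP variable list although it is collected. Objective 1 cannot be met in full as the SAP stands, whichever way A1.3 is read.

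The clusters may reflect pain severity rather than the stated profile. The size of that risk is open: illustrative recovery of personality groups runs from near zero to about 0.9. On the SAP's own grouping of instruments (about 8 against 24 scores) and with moderately correlated pain scores, it is near the low end. This rests on assumed score counts, group separation, correlations and k = 2. It should not be stated that the groups will be pain-severity groups. No alpha level, power or sample-size figure is affected.

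**What to change.** 1. Add named disease-history variables, taken from the primary disease, medical and treatment history already collected, to SAP 4.2 and 5.1.
2. In A1.3, run the objective 1 clustering only on standardised personality scores (MHLCS, HADS, LOT-R, Expectation) plus those variables. State how categorical history variables enter a k-means and how the number of clusters is chosen.
3. Extend tab-v1-clustering-desc to report pain, CPA, quality of life and sociodemographics by cluster, marked as external descriptors not used to form the groups.
4. Keep the broad PCA for outlier viewing. Any all-variable clustering can stay as a labelled extra.

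The cost is SAP wording, one longer table, and the coding of disease-history variables already on the case report form. No new data are needed. The coding needs some care, because history items are largely categorical and k-means works on numeric distances.
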